7.18 Details of Implant Placement

At the Baseline Visit, the implant placement procedure needs to be documented as follows (Table 2):

- Time since tooth was lost or removed (note, soft tissue coverage of the socket should be complete at baseline; i.e., Type 2 according to the categorization of Hämmerle et al., 2004);
- Type of healing procedure (subgingival or transgingival) and if soft tissue transplant was required;
- Bone quality according to the 4 different bone types described by Lekholm et al., 1985;
- Implant length;
- Details of the surgery (including site of implant placed);
- Details of augmentation procedures (e.g., bone graft used);
- Torque measurements if applicable;

 Stability of the implant after placement. The implant can be considered as primary stable or instable.

7.19 Provisional Crown Description

Details of the selected provisional need to be documented at Visit 4 (Table 2):

- Material of the provisional crown;
- If the provisional crown was loaded in occlusion,
- If soft tissue graft was used.

7.20 Final Crown Description

Details of the final crown need to be documented at Visit 5 (Table 2):

- Material of the final crown;
- If the final abutment was torqued to 35 Ncm with no rotational movement of the implant.

8 Evaluation of Adverse Events and Device Deficiency

8.1 Definition

A summary of the classification for AEs is provided in Table 5.

Table 5: Summary of the Classification for Adverse Events

Adverse events	Non-device related	Device or procedure related	
Non- serious	Adverse Event (AE)	Adverse Device Effect (ADE)	
Serious	Serious Adverse Event (SAE)	Serious Adverse Device Effect (SADE)	
		Anticipated	Unanticipated
		Anticipated Serious Adverse Device Effect (ASADE)	Unanticipated Serious Adverse Device Effect (USADE)

8.1.1 Adverse Event

An AE is defined as any untoward medical occurrence, unintended disease or injury, or any untoward clinical signs (including abnormal laboratory findings) in patients, users or other persons, whether or not related to the study device. This definition includes events related to the study device, or events related to the procedures involved. For users or other persons, this

definition is restricted to events related to study devices. Disease signs and symptoms already existing prior to the use of the study devices are not considered as AE unless they re-occur after the patient has recovered from the preexisting condition, or represent an exacerbation in intensity or frequency.

8.1.2 Serious Adverse Event

An AE should be classified as serious if it meets any of the following criteria:

- Led to a death;
- Led to a serious deterioration in the health of the patient, that either resulted in:
 - A life-threatening illness or injury, or
 - A permanent impairment of a body structure or a body function, or
 - o In-patient or prolonged hospitalization, or
 - Medical or surgical intervention to prevent life-threatening illness or injury or permanent impairment to a body structure or a body function;
- Led to fetal distress, fetal death, or a congenital abnormality or birth defect.

A planned hospitalization for a pre-existing condition, or a procedure required by the protocol, without serious deterioration in health, is not considered to be a Serious Adverse Event (SAE).

This includes DDs that might have led to an SAE if

- · suitable action had not been taken, or
- intervention had not been made, or
- if circumstances had been less fortunate.

These are handled under the SAE reporting system.

8.1.3 Device Deficiency

A DD is an inadequacy of a medical device with respect to its identity, quality, durability, reliability, safety or performance. DD include malfunctions, use errors and inadequate labeling.

Device Deficiencies can be classified into:

- DDs with Serious Adverse Device Effect (SADE) potential
- DDs without SADE potential.

A DD does not always lead to an AE. In addition, only DDs related to the study device need to be tracked by Clinical Research Team.

8.1.4 Adverse Device Effect

An ADE is an AE related to the use of a study device or procedure (e.g., surgery). This definition includes AEs resulting from insufficient or inadequate IfU, deployment, implantation, installation, or operation, or any malfunction of the study device. This definition includes any event resulting from use error or from intentional misuse of the study device. Any AE which the Investigator believes has even a possible relationship to the device will be classified as an ADE.

8.1.5 Serious Adverse Device Effect

A SADE is an ADE that has resulted in any of the consequences characteristic of a SAE (see Section 8.1.2).

8.1.6 Unanticipated Serious Adverse Device Effect

An Unanticipated Serious Adverse Device Effect (USADE) is a SADE which by its nature, incidence, severity or outcome has not been identified in the current version of the Risk Management Report or IfU (Annex 1).

8.1.7 Anticipated Serious Adverse Device Effect

An Anticipated Serious Adverse Device Effect (ASADE) is an SADE which by its nature, incidence, severity or outcome has been identified in the Risk Management Report or IfU (Annex 1).

8.2 Assessment of Adverse Events

If an AE occurs, the Investigator or another suitably qualified clinician who is trained in recording and reporting AEs and have been delegated to this role (such delegation must be captured in the Study Site Delegation Log) must review all documentation (e.g., hospital notes, laboratory and diagnostic reports) relevant to the event.

Each AE should be assessed by the Investigator for seriousness, relationship to the study device or the procedure, severity, expectedness and outcome as described in Sections 8.2.1 to 8.2.5. The rationale for each assessment must be described as well in a short paragraph and source documents should support the designation. To do so, the Investigator reviews systematically all available documentation (e.g., hospital notes, X-rays, laboratory and diagnostic reports) relevant to the event and investigates its cause.

8.2.1 Seriousness

An AE will be described as serious if it meets the definition in Section 8.1.2.

8.2.2 Relationship to the Study Device or Procedure

It is useful to analyze an AE in accordance with the time of its occurrence and the surgery date (i.e., during the implantation period of the device, application, or attempt of placement).

8.2.2.1 Relationship to the Study Device

The Investigator will make an assessment of whether the AE is likely to be related to the device according to the following definitions:

- Definitely Related there is a reasonable causal and temporal relationship between the study device and the AE.
- **Possibly Related** the nature of the event or temporal relationship make it possible that the AE has a causal relationship to the device.
- Not Related no obvious relationship between the study device and the AE.

8.2.2.2 Relationship to the Procedure

The Investigator should assess the relationship of the AE to the implant procedure (e.g., placement of dental implant). The relationship should be assessed using the categories described in Section 8.2.2.1.

8.2.3 Severity

Each AE should be assessed by the Investigator for its severity, or the intensity of an event experienced by a patient, according to the following categories:

- Mild events are usually transient, requiring no special treatment, and do not interfere
 with the patient's daily activities.
- Moderate events that introduce a low level of inconvenience or concern to the patient and may interfere with daily activities, but are usually ameliorated by simple therapeutic measures
- Severe events interrupt a patient's usual daily activity and traditionally require systemic drug therapy or other treatment.

The term "severe" used to describe the intensity of an event should not be confused with the term "serious", as defined in Section 8.1.2.

8.2.4 Expectedness

If the AE is judged to be related to the study device or procedure, i.e., is an ADE, the Investigator will make an assessment of expectedness, or anticipation, based on knowledge of the reaction and any relevant product information as documented in the IfU (Annex 1) or in the

list of potential expected ADEs in the current protocol (Table 6) following the insertion of dental implants. The event will be classed as either:

- Expected the reaction is consistent with the effects of the device listed in the IfU
 (Annex 1) or list of potential expected ADEs in the current protocol (Table 6) following the insertion of dental implants.
- Unexpected the reaction is not consistent with the effects listed in the IfU (Annex 1) or list of potential expected ADEs in the current protocol (Table 6) following the insertion of dental implants.

Table 6: List of Potential Expected Adverse Device Effects Following the Insertion of Dental Implants

Biological complications

Peri-implant mucositis

- Bleeding (bleeding on probing)
- Bruising
- Mucosal/gingival inflammation (=gingivitis/mucositis, inflammation of the gum tissue)/redness
- Gingival enlargement (=gingival hyperplasia, gingival hypertrophy, gum overgrowth, hypertrophic gingivitis)
- Gingival recession (=dehiscence of the gingiva, receding gums)
- Pain (discomfort)
- Suppuration
- Swelling

Peri-implantitis

- Bleeding (bleeding on probing)
- Bone loss around implant (=peri-implant bone loss)
- Bruising
- Infection at implant site without suppuration
- Infection at implant site with suppuration (=peri-implant abscess)
- Systemic infection
- Pain
- Swelling

Bone integration deficiency

- No primary stability (at surgery)
- Implant mobility (tactile horizontal or vertical)
- Early loss/failure of implant (i.e. before osseointegration) (=primary implant failure)
- Late loss/failure of implant (i.e. after osseointegration) (=secondary implant failure)
- Radiolucency
- Aspiration of implant
- Swallowing of implant

Non-plaque related

- Foreign body sensation
- Material allergy
- Oro-sinus or oro-nasal intrusion/fistula
- Permanent paresthesia/dysesthesia
- Temporary or permanent nerve damage in the jaw

Mechanical complications

- Loosening of abutment or prosthetic screw
- Loosening of an healing cap
- Loss/failure of an abutment
- Loss/failure of an healing cap
- Fracture of abutment or prosthetic screw
- Fracture of implant

Technical complications

- · Fracture of prosthesis or veneer
- Irreversible damage to adjacent/opposing teeth
- · Loss of cement retention of prosthesis

Other complications

- Esthetic problem
- Aspiration of component(s) (other than implant)
- Jaw. bone fracture
- Phonetic difficulties
- Swallowing of component(s) (other than implant)
- Hypersensitivity (adjacent teeth)

8.2.5 Outcome

The outcome should reflect the status of the AE at the moment of recording.

- **Resolved without Sequelae** the patient fully recovered from the event without any sequelae. This option also applies when it is unknown whether there are sequelae.
- Resolved with Sequelae the patient's condition stabilized despite the persistence of sequelae (e.g., lesion or medical condition which is a consequence of the event). This option does not apply to irreversible congenital anomalies (see under "ongoing").
- Ongoing the patient has not yet recovered from the event. By convention, in the case of
 an irreversible congenital anomaly, the "ongoing" option should be chosen and understood
 as "Not recovered/Not resolved". The same applies to conditions that are not yet resolved,
 but are controlled by medication (e.g., diabetes, epilepsy) and therefore may not have any
 symptoms.
- Worsened the severity of the event increased.

- **Fatal** the event is related to a death; whether it caused death or contributed to it. If the patient died of a different cause, prior to resolution of the event, the outcome of this event should designated "ongoing", and not "fatal", and an end date should not be specified.
- Unknown knowledge of the current status of the event is truly not available to the
 Investigator (i.e., event was ongoing at last observation, but no further contact with the
 patient could be established). However, all efforts should be made to determine the
 outcome of any event, especially that of an SAE/SADE.

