8.4 Monitoring of Patients with Adverse Events

Any AE that occurs during the course of this study must be monitored and followed-up by the Investigator until one or more of the following have occurred:

- The AE is resolved,
- Pathological laboratory findings have returned to normal,
- Steady state has been achieved, or
- It has been shown to be unrelated to the study devices.

The outcome of an event will be pursued until resolution or until the last data queries are issued following the patient's last study visit. For screening failures, ongoing AEs, ADEs and DDs must be followed and updated until the date the patient is deemed a screening failure. For patient documented as lost to follow-up, ongoing AEs, ADEs, and DDs will not be followed.

It is the responsibility of the sponsor to cooperate with the Investigator to assure that any necessary additional therapeutic measures and follow-up procedures are performed.

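### The outcome code for full recovery also takes in events whose sequelae are unknown, so any summary of adverse events by outcome can overstate full recovery

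*Combined protocol and SAP*

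**What the plan says.** Section 8.2.5 (Outcome) lists the categories the Investigator may choose for each adverse event. Four matter here.

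- *Resolved without Sequelae*: "the patient fully recovered from the event without any sequelae". The definition continues: "This option also applies when it is unknown whether there are sequelae".
- *Resolved with Sequelae*: the patient's "condition stabilized despite the persistence of sequelae".
- *Ongoing*: "the patient has not yet recovered from the event".
- *Unknown*: "knowledge of the current status of the event is truly not available" to the Investigator. The case given is an event still ongoing when last seen, after which contact was lost.

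Section 8.2 asks for a short written rationale for each assessment, including outcome, and expects source documents to back the category chosen. Section 3.4.2 names the safety endpoint as the incidence of AEs and ADEs. Section 9 plans descriptive statistics in general terms and does not specify a table by AE outcome.

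**The concern.** The two sentences of the first definition do not fit together. The first asserts full recovery; the second assigns the same code when the fact that would justify the assertion is missing. Missing information is thus stored as the best result. It is also stored as a complete, valid entry, so the outcome field itself gives data management no reason to raise a query under Section 11.4.4.

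At stake is how far the recorded outcomes can be trusted in a study whose stated aim (Section 2) includes safety data. It plans at least 40 patients and a purely descriptive analysis. With few events, the coding of one or two can visibly change a breakdown by outcome.

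**Working it through.** No figure in the documents depends on this rule, so there is nothing to reproduce. The check is to see where each kind of event goes under Section 8.2.5.

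| State of the event | Code under Section 8.2.5 |
|---|---|
| Ended, absence of sequelae confirmed | *Resolved without Sequelae* |
| Ended, sequelae not ascertained | *Resolved without Sequelae* |
| Ended or stabilized, sequelae known | *Resolved with Sequelae* |
| Not recovered | *Ongoing* |
| Current status unavailable | *Unknown* |

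The first two rows share a code. The second row cannot go to *Unknown*, because the current status of such an event is known: it has ended. What is missing is a different fact, whether anything was left behind.

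**Direction of the error.** Among *n* ended events, let *c* be confirmed free of sequelae, *s* have known sequelae and *u* be unascertained, so that *n* = *c* + *s* + *u*. Under the rule the share reported without sequelae is (*c* + *u*)/*n*. The confirmed share is *c*/*n*. The true share lies between *c*/*n* and (*c* + *u*)/*n*, depending on how many of the *u* events left sequelae. The rule always reports the upper limit, so it can overstate full recovery by up to *u*/*n* and can never understate it through this route.

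**Size.** The documents give no value or expected rate for *u*, and none can be derived from them.

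**Can *u* be above zero here?** Three features make it plausible:

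- Section 8.3.2 recognizes that many SAEs will be treated in a medical rather than a dental setting, where the Investigator may not learn of them at once.
- Section 11.3.5 requires withdrawal after implant loss, so such a patient may have no later study visit.
- Table 6 includes the term "Temporary or permanent nerve damage in the jaw", which does not itself say whether the damage lasted.

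**Fit with Section 8.2.** A full-recovery code chosen because sequelae are unknown cannot be supported by source documents in the way that section expects.

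**The case against.** The strongest reply is that this is a wording flaw in one definition with little reach. Most of that reply stands.

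A reader might infer that permanent harm from the implant would be reported as full recovery. The documents do not support this. Harm known to persist goes to *Resolved with Sequelae* or *Ongoing*, and several Table 6 terms, such as permanent paresthesia, already state persistence. Only sequelae that were never ascertained are affected.

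A reader might also infer that serious events would escape expedited reporting, because "A permanent impairment of a body structure or a body function" is one of the seriousness criteria in Section 8.1.2. But seriousness is a separate assessment (Section 8.2.1), and nothing makes it, or the 24-hour requirement, depend on the outcome code.

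Nor does the rule shut off re-assessment. New AEs are sought at every visit (Section 7.16), and the success criteria at Visits 5, 6 and 7 cover persisting discomfort, dysesthesia, mobility and radiolucency (Section 7.13). AE pages can be updated (Section 8.3). Follow-up under Section 8.4 can also end when a steady state is reached, so the sentence in Section 8.2.5 is not what closes an event. Section 8.4 further says "For patient documented as lost to follow-up, ongoing AEs, ADEs, and DDs will not be followed", but that concerns ongoing events, which *Unknown* already covers when contact is lost.

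Finally, the written rationale required by Section 8.2 might let someone separate the two groups by reading each entry. That is free text, not an analysis variable, and the outcome code alone does not allow the separation.

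What the reply does not remove is the definition itself. It directs unknown sequelae to the full-recovery code, and no neutral code exists.

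**Conclusion.** The point holds as a data-definition error. Confirmed absence of sequelae and unascertained sequelae are merged in the most favourable category, and any summary by outcome can be biased in one direction, towards full recovery.

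Its reach is limited. AE and ADE incidence does not use the outcome code, the primary endpoint is implant survival, and seriousness and known permanent harm are handled elsewhere. The effect appears only if AEs or ADEs are summarized by outcome, which Section 9 neither specifies nor rules out. Its size is *u*/*n* at most, and the documents give no basis for a number. The conclusion rests on the text of Section 8.2.5 and on no assumed event rate. The correction is worth making because it is nearly free and the bias has a known direction.

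**What to change.** 1. In Section 8.2.5, delete the sentence "This option also applies when it is unknown whether there are sequelae" from *Resolved without Sequelae*.
2. Add an outcome *Resolved, sequelae unknown*. Alternatively, extend *Unknown* to events that have ended but whose sequelae were not established. A separate option is cleaner, because extending *Unknown* would mix these events with those whose status is unavailable unless a flag tells them apart.
3. State that any table by outcome shows this group on its own line.

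The cost is one sentence, at most one extra eCRF option, and possibly a slightly lower reported share resolved without sequelae. If events have already been coded under the present wording, the rationale text required by Section 8.2 can be used to review those entered as resolved without sequelae.

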8.3 Procedure for Reporting Adverse Events and Device Deficiencies

Adverse Event reporting will begin at the start of implant placement at the Baseline Visit until the last protocol-specific procedure of a patient. All AE/SAEs should be collected, fully investigated and documented in the source document and appropriate eCRF pages for all patients. In the eCRF, only 1 AE/SAE eCRF entry should be completed per event. To ensure patient confidentiality, the reports in Sections 8.3.1 to 8.3.6 will include the patient number only.

The report sequence "initial" shall be ticked on the eCRF page for the initial AE report. In order to capture the new information, the AE eCRF page shall be updated and the report sequence "follow-up" or "final" shall be ticked as appropriate.

Adverse Events like swelling, pain or bleeding do not need to be captured on the eCRF page as long as they occur in the same or milder intensity as during standard treatment during the following procedures:

- Visit 2: implant placement
- Visit 3: suture removal
- Visit 4: Placing of the provisional crown
- Visit 5: Placing of the final crown

8.3.1 Adverse Event Reporting

In the occurrence of an AE, the AE eCRF page should be completed in a timely manner. Safety reporting to the local EC should occur according to the requirements of the EC (see Section 11.3.3).

8.3.2 Serious Adverse Event Reporting

In the occurrence of a SAE, expedited reporting requirements are followed. The AE eCRF page should be completed within 24 h of awareness of the event. The Investigator needs to follow-up on all ongoing SAEs until resolution. In case of a break-down of the eCRF system,

an SAE/SADE Report Form needs to be completed for each event and sent to the sponsor within 24 h of awareness of the event:

Contact address:

Clinical Research, Institut Straumann AG

[contact] [contact]

Email: [contact]

Safety reporting to the local EC should occur according to the local requirements (see Section 11.3.3).

It is recognized that in many cases SAEs will be treated in a medical rather than a dental environment and the Investigator may not have immediate knowledge of the event. The Investigator should report an SAE as soon as he/she has knowledge of the event within the above time frame irrespective of when the actual event occurred.

8.3.3 Device Deficiency Reporting

In the occurrence of a DD, the DD eCRF page should be completed in a timely manner. When a DD leads to a potential AE (e.g., bleeding, pain, swelling, infection, peri-implantitis) the AE eCRF page needs to be completed in a timely manner as well. Moreover, DD with SADE potential (e.g., nerve encroachment, sinus perforation, etc.) must be recorded on the AE eCRF page, follow the expedited reporting requirements (within 24 h) and the Investigator needs to follow-up until resolution. In case of a break-down of the eCRF system, an SAE/SADE Report Form needs to be completed for each event and sent to the sponsor within 24 h of awareness of the event:

Contact address:

Clinical Research, Institut Straumann AG

[contact] [contact]

Email: [contact]

8.3.4 Adverse Device Effects Reporting

Adverse Device Effects must be recorded by completing the AE eCRF page in a timely manner. The Investigator needs to follow-up on all ongoing ADEs until resolution. Safety reporting to the EC should occur according to the local requirements (see Section 11.3.3).

Continuous substantial reduction of the peri-implant bone level is a sign of failure of the implant system. The 1st European Workshop on Periodontology specified an average marginal

bone loss of less than 1.5 mm bone loss within the 1st year after the insertion of the prosthesis, and thereafter less than 0.2 mm annual bone loss as criteria for measuring success (Albrektsson et al., 1993). This has been a standard and a basis for success criteria since it was defined in 1993. In a more recent meta-analysis, the authors looked at Straumann implants and determined that a pooled weighted mean of marginal bone level change for Straumann implants was -0.56 mm (95% CI -0.661 to -0.481) after 5 years. The individual study means of marginal bone level change ranged from -1.0 to -0.15 mm after 5 years (Laurell L et al., 2011). Based on this information the central radiologist will flag any bone level changes that are greater than 2.0 mm in the 1st year after insertion of the prosthesis.

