3.4.2 Secondary Endpoints

The following parameters will be measured as secondary endpoints:

- PES at 6 months after implant placement
- Implant success at 12 months after implant placement
- · Marginal bone level changes at 12 months after implant placement
- AEs and ADEs incidence

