7.12.1 Bone Level Changes

Peri-apical X-rays are standard procedures during implant surgery to assess changes of the bone level. Peri-apical X-rays will be taken at baseline (Visit 2), at placement of the final crown (Visit 5) and at the end of the study (Visit 7) to assess bone level changes between implant placement (Baseline Visit) and placement of the final crown (Visit 5) as well as between implant placement and the 12-month Follow-Up Visit (Visit 7) (Table 2).

An independent expert will be contracted to perform the bone level measurements from the X-rays. The vertical bone level will be evaluated by measuring the distance from the implant shoulder to the first visible bone contact on the implant. Measurements will be taken at the mesial and distal aspects of the implant, and an average value will be calculated. Mean bone level changes will be computed by subtracting the average bone level at Visit 5 from the average bone level at baseline (implant placement) and by subtracting the average bone level at the 12-month Follow-Up Visit (Visit 7) from the average bone level at baseline (implant placement). Hence, negative bone level changes are representing bone loss between baseline and Visit 5 and between baseline and the 12-month Follow-Up Visit, respectively; vice versa positive changes representing bone gain. Measurements will take into account distortion based on changes on the radiograph from the true dimension of the implant.

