7.16 Adverse Events

At each visit the Investigator should determine if any AEs occurred since the last study visit by speaking with the patient and reviewing any dental and medical records. These AEs, along with any AEs from the current study visit, should be documented and reported as described in Section 8 of the protocol. In addition the Investigator should evaluate the status of any ongoing AEs throughout the study as specified in Section 8.4.

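### Does the unnamed reference film for the 2.0 mm bone-level flag in Section 8.3.4 put the ADE incidence at risk?

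*Combined protocol and SAP*

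**What the plan says.** Section 8.3.4 sits within the ADE reporting rules. It cites a 1993 workshop criterion of average marginal "bone loss of less than 1.5 mm bone loss within the 1st year after the insertion of the prosthesis", adds a later meta-analysis, and concludes that "the central radiologist will flag any bone level changes that are greater than 2.0 mm in the 1st year after insertion of the prosthesis".

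Section 7.12.1 governs the measurement. After the baseline film, peri-apical films are taken "at placement of the final crown (Visit 5) and at the end of the study (Visit 7"). They serve to measure "bone level changes between implant placement (Baseline Visit) and placement of the final crown (Visit 5) as well as between implant placement"; the second of these intervals closes at Visit 7. Loss carries a negative sign. No change from Visit 5 to Visit 7 is defined.

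On the safety side, Section 8.3 states: "Adverse Event reporting will begin at the start of implant placement at the Baseline Visit until the last protocol-specific procedure of a patient". Under Section 7.16 the Investigator looks for events at each visit "by speaking with the patient and reviewing any dental and medical records". Table 6 in Section 8.2.4 lists "Bone loss around implant (=peri-implant bone loss") as a potential expected ADE, and Section 3.4.2 makes "AEs and ADEs incidence" a secondary endpoint.

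**The concern.** The flag's time phrase can mark the start of the change, or only the period in which a change is flagged. The cited 1993 criterion uses nearly the same phrase, which favours a start at the prosthesis; Section 7.12.1 starts at implant placement. The schedule also has two crowns, provisional at Visit 4 and final at Visit 5, and the sentence names neither.

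Counted from the final crown, the Visit 5 film is the starting film. Early loss is then outside the flag whatever its size, and only the last film of the study can raise one, at the visit where AE reporting closes. No passage says how a flag reaches the Investigator or the AE page. The success criteria in Section 7.13 contain no amount of bone loss, so this flag is the only rule that picks out individual patients by how much bone they lost. If flags feed the ADE records, the incidence of a secondary endpoint would depend on an unstated reading.

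**Working it through.** The 2.0 mm threshold is set, not derived, so there is no plan figure to reproduce. The check is visit-window arithmetic plus the change formula.

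**Inputs.** Visit 4 at 6 ± 2 weeks, Visit 5 at 4 ± 1 months, Visit 7 at 12 ± 1 months (Section 6.1, Table 3). Films at Visits 2, 5 and 7 only (Section 6, Table 2). Change = earlier level minus later level, loss negative (Section 7.12.1).

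**Step 1: which changes exist.** With levels L2, L5 and L7:

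- d25 = L2 − L5
- d27 = L2 − L7
- d57 = L5 − L7 = d27 − d25

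There is no Visit 4 film, so the provisional crown cannot start a measured change; it can only open the flagging period. Three readings remain:

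- A: change from the final crown, d57.
- B: change from placement, flagged once the final crown is in: d27, and also d25 where the Visit 5 film follows insertion. Section 6.7 provides for that order when a general dentist places the crown, and no passage puts the film before the crown otherwise.
- C: change from placement, flagged once the provisional crown is in: d25 and d27.

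**Step 2: timing.**

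| Quantity | Low | Nominal | High |
|---|---|---|---|
| Visit 5 to Visit 7 (months) | 11 − 5 = 6 | 12 − 4 = 8 | 13 − 3 = 10 |
| As share of 12 months | 50% | 67% | 83% |
| Share of time from placement to Visit 7 that precedes Visit 5 | 3/13 = 23.1% | 4/12 = 33.3% | 5/11 = 45.5% |

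**Step 3: do the readings disagree?** Invented patients, flagged if the change is below −2.0 mm:

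| d25, then d57 (mm) | d27 (mm) | A | B | C |
|---|---|---|---|---|
| −2.3, 0.0 | −2.3 | no | yes | yes, already at Visit 5 |
| −1.2, −1.0 | −2.2 | no | yes | yes |
| +0.5, −2.3 | −1.8 | yes | no | no |

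So they can disagree, in both directions. The identity in Step 1 shows that all three changes are available for any patient with the three scheduled films, so no reading is closed off by the data collected.

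**Step 4: from flag to ADE record.** Section 8.3.4 does not say that a flagged change is an ADE. Section 8.2 gives the assessment to the Investigator and names X-rays among the documents to review. Radiographs are source documents (11.4.2) and the originals stay at the center (11.4.5), so the site holds the Visit 5 film 6 to 10 months before Visit 7. The Visit 7 film belongs to the same visit as the last AE assessment (6.9), and loss visible on it arose during the reporting period. Section 11.4.4 raises queries on missing or questionable data and freezes the database only once they are answered.

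**Step 5: size.** One patient in 40 is 1/40 = 2.5 percentage points of ADE incidence. That is the most one patient can contribute, and only if that patient has no other ADE.

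**The case for a change.** The strongest contrary case is that the contradiction is on the page and cheap to remove. Section 8.3.4 implies a start that Section 7.12.1 never defines, the reader is an independent expert in one place and a central radiologist in the other, and the reading decides who is flagged. Section 8.4 pursues outcomes after the last visit only for events already open, so a new event found by late central reading has no written route. Section 8.3.4 itself treats continuous substantial bone reduction as a sign of implant failure, so such a signal ought not to depend on custom.

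The ambiguity and the unwritten route stand. The consequences do not carry the same weight. Early loss escapes the flag only under reading A; Section 7.12.1 still has it measured. The statement that only the Visit 7 film can raise a flag is secure for A but not for B, given Section 6.7. Late entry is not provided for, but it is not barred either. A flag placed in the ADE reporting section already implies that the Investigator is told, and a sponsor would normally do that by query. Naming the visits would record the sponsor's own choice; it would not correct an analysis.

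**Conclusion.** This is missing detail that those running the study can fill sensibly; it is not a flaw in the plan. The primary endpoint (survival), implant success and the 12-month bone level change use their own definitions and are untouched. Section 9 makes the analysis descriptive, so no test or decision turns on the flag. The exposed quantity is ADE incidence, by at most 2.5 percentage points per patient classified differently, and only if flags lead to ADE records.

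How many patients that would be is unknown. The bone-level figures in Section 8.3.4 (pooled mean −0.56 mm, study means −1.0 to −0.15 mm, at 5 years) are means without an SD and cannot give a frequency.

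The conclusion assumes that central readings are available before the freeze and that flags are passed to the Investigator. The Data Management Plan and Monitoring Plan may cover this, but they are not among the documents. Which crown and which threshold apply is for the sponsor to decide.
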